7 STUDY PROCEDURES AND SCHEDULE

7.1 OVERVIEW OF DATA COLLECTION

The following main types of data will be collected in this study:

Efficacy data

- Data concerning the sBCC target lesions and the treated area(s) (number, size, location).
- Data concerning the esthetic outcome/appearance of the treatment field(s).
- Data concerning subject's satisfaction.

Safety data

- Frequency and duration of adverse events (AEs), serious AEs (SAEs), and treatment-emergent adverse events (TEAEs). TEAEs are defined as all AEs with onset or worsening after treatment with randomized IMP within 4 weeks after each PDT cycle (until Visit 4 or Visit 7, respectively).
- New NMSC and melanoma, including location of lesion(s).
- New AK lesions including location of lesion(s).
- Local skin reactions at the treatment field(s), assessed by the investigators.
- Local discomfort and pain during or after illumination, reported by the subjects.
- Vital signs (blood pressure (BP), heart rate (HR)).
- Standard laboratory safety data (hematology, biochemistry and urinalysis).
- Data from physical examinations.

Other data

- Demographic data.
- Skin type assessment.
- Biopsy data of BCC lesions and histological examination for confirmation of diagnosis
- Excision of Main Target BCC Lesion and results of histopathological examination.
- Treatment of remaining or recurrent Additional Target Lesions
- Medical history.
- Concomitant medications/treatments.

7.2 DESCRIPTION OF STUDY DAYS

The study schedule is provided in [Table 1](#) and is furthermore depicted in Figure 1.

7.2.1 Clinical observation phase

Visit 1, Screening (≤ 4 weeks prior to PDT-1)

Potential subjects will be evaluated to determine whether they fulfill the inclusion and exclusion criteria (see [Sections 4.3](#) and [4.4](#)). The following additional evaluations and procedures will be performed at Visit 1 (Screening):

- Subject will be informed about the study and signs the informed consent agreement and the HIPAA form for study participation. The signed consent must be available prior to any other study-related procedures.
- Assignment of subject number (randomization number will be assigned at Visit 2).
- Evaluation and documentation of demographic data.
- Evaluation of inclusion and exclusion criteria.
- Documentation of relevant medical history and concomitant medication (see [Section 6](#)).
- Assessment of the skin type according to Fitzpatrick (see [Appendix A](#))⁽¹⁾.
- Documentation of skin disease history, including NMSC and melanoma history.
- Documentation of current AK, NMSC and melanoma status, including location of lesion(s).
- Clinical assessment of sBCC lesions (location(s), size (minimal diameter 0.6 cm, for the Main Target Lesion the maximal diameter should be limited by the suitability for surgical excision at the end of the clinical observation period, please refer also to *Definition of Target Lesions, illumination and treatment region*, [Section 7.3.1](#)). The combined treatment field(s) should not exceed 20 cm² (including 0.5 – 1.0 cm margins surrounding the target lesion(s)) (see [Section 4.3](#)).
- Generation of a template (on provided grid foil) to locate and mark the target lesions to be treated relative to specific body marks. Additional recording of target lesions shall be indicated on the body map cartoon provided together with the grid foil (to be kept in subject file).
- Biopsies (3 mm punch biopsies) of selected clinically diagnosed sBCC to histologically confirm the diagnosis. Biopsy must be unambiguously assigned to the specific target lesion and sent to the central dermatopathological laboratory for evaluation. Containers and fixation solution will be provided to the centers by the central dermatopathological laboratory. In order to minimize the burden of the subject, 3 mm punch biopsies taken within a period up to 2 months prior to screening can be considered. In this case, slides and/or blocks, or digitalized images of slides/blocks, of the specified lesion(s) should be sent to the central dermatopathological laboratory for re-evaluation taking an accurate pseudomysation of the subject's data into account. The samples/images will be assessed according to the WHO criteria for the histological typing of skin tumors⁽²⁾.
- Withdrawal of blood and collection of urine samples for clinical laboratory tests and urinalysis.
- Serum pregnancy tests for female subjects of reproductive potential.
- General physical examination.

- Measurement of vital signs (HR and BP).
- Subject should be reminded about allowed and forbidden medications (see below)
- Investigator will send a subject status confirmation by FAX or email.

The inflammation induced by the PDT is an important part of the therapeutic mode of action and is intended. Therefore, the investigator should advise the subject about the following restrictions prior and after each PDT:

Up to 7 days prior to PDT, intake and/or any other systemic treatment with NSAIDs is not to be used. ASA up to 100 mg/day, ibuprofen up to 200 mg/day is allowed in this period. Topical NSAIDs such as diclofenac are not to be used 7 days prior to each PDT in- and outside the treatment fields. Topical treatments with corticosteroids are allowed throughout the clinical phase of the study.

After PDT, analgesic treatment with acetaminophen (e.g. Tylenol®) may be indicated and is allowed.

The following therapies should not be used to treat pain and discomfort **during and up to 7 days after the PDT**:

- Systemic
 - Acetylsalicylic acid >100 mg/day
 - NSAIDs such as diclofenac or ibuprofen (>200 mg/day)
 - Corticosteroids
- Topical
 - EMLA® cream
 - NSAIDs such as diclofenac

The subject should be informed about these restrictions accordingly.

The following evaluations and procedures will be performed at either the study visits or through the phone contact:

Visit 2, PDT-1 (Baseline)

- Double check all inclusion and exclusion criteria, in particular the confirmation of diagnosis of sBCC for at least one lesion based on the result of the histopathological evaluation. The subject must not be randomized if no lesion fulfills the criteria or if all eligible lesions are located closer than 5 cm to one of the non-suitable BCC lesions.
- Randomization and assignment of randomization number.
- Assessment of the sBCC lesion(s) (lesion count, location, and size).
- Measurement of vital signs (HR and BP).
- Pregnancy test (urine) for females of reproductive potential.

- Definition of the Main Target Lesion and application of at least 3 ink marks to establish its exact position. Further lesions included in the study will be regarded as Additional Target Lesions. The Main Target Lesion should be representative for the eligible lesions of the subject and should take the burden for the subject into account. However, for the Main Target Lesion, the maximal lesion size should be such that surgical excision without a skin transplant is feasible according to the investigator's judgement. In cases where two or more lesions would qualify as Main Target Lesion, the lesion whose excision will cause the least burden for the subject shall be selected. (Please refer also to *Definition of Target Lesions, illumination and treatment region*, [Section 7.3.1](#))
- Thorough preparation of eligible lesions and application of IMP (see [Section 5.1.2](#)).
- Documentation of time of IMP application and removal.
- All target lesion(s) will be illuminated with BF-RhodoLED® until a total light dose of 37 J/cm² per treatment field is achieved. In cases of severe pain, illumination may be shortly interrupted, e.g. to inject a fast acting local anesthetic, such as xylocaine (see [Section 5.1.3](#)).
- Documentation of illumination procedures, including time of illumination (10 min) and distance of the LED lamp to the treated lesion(s) (5-8 cm). Additional documentation of possible pain induced interruptions (duration, frequency) and pain relieving measures during illumination. Deviations from the standard illumination procedure have to be justified.
- Pain reported by the subject during the illumination will be recorded using the numeric rating pain scale (NRPS) by the provided subject's pain questionnaire (see [Section 7.3.2](#)).
- Discomfort reported by the subject during the illumination will be recorded by the provided subject's discomfort questionnaire (see [Section 7.3.2](#)).
- Documentation of AEs, including local skin reactions, local discomfort, and pain during and/or after PDT at the treatment field(s).
- Documentation of new AK, NMSC and melanoma, including location of lesion(s).
- Documentation of concomitant medications/treatments including those, which might be taken for pain management during and/or after PDT.
- Subject should be reminded about allowed and forbidden medications (see [Visit 1](#)).
- Investigator will send a subject status confirmation by FAX or email.

Visit 3, PDT-2 (1-2 weeks post PDT-1 (Visit 2))

- Assessment of how the subject is feeling since last PDT. Using non-leading questions such as "How did you feel since your photodynamic treatment session", the investigator or delegated person will evaluate any discomfort the subject may be experiencing. Any reported AE or concomitant treatment will be documented.
- Measurement of vital signs (HR and BP).
- Pregnancy test (urine) for females of reproductive potential.
- Thorough preparation of the treated BCC target lesion(s) and application of IMP (see [Section 5.1.2](#)).
- Documentation of time of IMP application and removal.

- The target lesion(s) will be illuminated with an LED lamp (BF-RhodoLED®) until a total light dose of 37 J/cm² (per treatment field) is achieved. In cases of severe pain, illumination may be shortly interrupted, e.g. to inject a fast acting local-anesthetic, such as xylocaine (see [Section 5.1.3](#)).
- Documentation of illumination procedures, including time of illumination (10 min) and distance of the LED lamp to the treated lesion(s) (5-8 cm). Additional documentation of possible pain induced interruptions (duration, frequency) and pain relieving measures during illumination. Deviations from the standard illumination procedure have to be justified.
- Pain reported by the subject during the illumination will be recorded using the NRPS by the provided subject's pain questionnaire (see [Section 7.3.2](#)).
- Discomfort reported by the subject during the illumination will be recorded by the provided subject's discomfort questionnaire (see [Section 7.3.2](#)).
- Documentation of AEs, including local skin reactions, local discomfort, and pain during and/or after PDT at the treatment field(s).
- Documentation of new AK, NMSC and melanoma, including location of lesion(s).
- Documentation of concomitant medications/treatments including those, which might be taken for pain management during and/or after PDT.
- Subject should be reminded about allowed and forbidden medications (see [Visit 1](#)).

Phone call 1 (1 week ± 2 days post-PDT-2 (Visit 3))

The aim of this safety telephone contact is to achieve an overall impression on the tolerability of the PDT with the study drug and to evaluate how the subject is feeling since the last PDT session. Using non-leading questions such as "How did you feel since your photodynamic treatment session", the investigator or delegated person will evaluate any discomfort the subject may be experiencing. Any reported AE or concomitant treatment will be documented.

The following information will be collected during each phone contact:

- Concomitant medications/treatments.
- (S)AEs, including local skin reactions, local discomfort, and pain at the treatment field(s).

Visit 4 (5 weeks ± 1 week post-PDT-1 (Visit 2))

- Assessment of Main Target Lesion and Additional Target BCC Lesion(s) (count, size, and location).
- Measurement of vital signs (HR and BP).
- Documentation of AEs, including local skin reactions, local discomfort, and pain at the treatment field(s).
- Documentation of new AK, NMSC and melanoma, including location of lesion(s).
- Documentation of concomitant medications/treatments.

- Subject should be once again informed about the possibility of a 2nd PDT cycle at visit 5 and thus about restrictions concerning intake of certain medications 7 days prior to/after PDT (see [Visit 1](#)).

Visit 5, PDT-3 (12 weeks ± 1 week post-PDT-1 (Visit 2))

- **For complete responders (i.e., subjects with all treated target lesions [Main and Additional Target Lesions] clinically cleared):** End of clinical observation period of the study for these subjects.
- Assessment of treated BCC target lesion(s) (count, size, and location).
- Assessment of esthetic appearance of the treated lesions (treatment field(s)) by investigator prior to excision.
- Assessment of subject's satisfaction regarding PDT treatment and esthetic outcome prior to excision.
- Measurement of vital signs (HR and BP).
- Documentation of AEs, including local skin reactions, local discomfort, and pain at the treatment field(s).
- Documentation of new AK, NMSC and melanoma, including location of lesion(s).
- Documentation of concomitant medications/treatments.
- General physical examination.
- Withdrawal of blood and collection of urine samples for safety laboratory tests and urinalysis.
- Pregnancy test (urine) for females of reproductive potential.
- Excision of the Main Target Lesion including ink-marks and histological assessment.
- Subjects will be asked to return for the 1st FU visit in approx. 12 months (12 ± 1 months post completion of 1st PDT cycle).
- Investigator will send a subject status confirmation by FAX or email.

For partial- or non-responders (not all target lesions are clinically cleared): Start of 2nd PDT cycle.

- Assessment of the treated BCC target lesion(s) (lesion count, size and location).
- Measurement of vital signs (HR and BP).
- Pregnancy test (urine) for females of reproductive potential.
- If the Main Target Lesion is assessed as clinically cleared:
 - Assessment of esthetic appearance of the Main Target Lesion by investigator prior to excision.
 - Assessment of subject's satisfaction of esthetic outcome of the Main Target Lesion prior to excision.
 - Excision of the Main Target Lesion including ink-marks and histological assessment.

- Thorough preparation of all remaining target lesion(s) included in the study and application of IMP (see [Section 5.1.2](#)).
- Documentation of time of IMP application and removal.
- All lesion(s) that are not yet clinically cleared will be illuminated with an LED lamp (BF-RhodoLED[®]) until a total light dose of 37 J/cm² (per treatment field) is achieved. In cases of severe pain, illumination may be shortly interrupted, e.g. to inject a fast acting local-anesthetic, such as xylocaine (see [Section 5.1.3](#)).
- Documentation of illumination procedures, including time of illumination (10 min) and distance of the LED lamp to the treated lesion(s) (5-8 cm). Additional documentation of possible pain induced interruptions (duration, frequency) and pain relieving measures during illumination. Deviations from the standard illumination procedure have to be justified.
- Pain reported by the subject during the illumination will be recorded using the NRPS by the provided subject's pain questionnaire (see [Section 7.3.2](#)).
- Discomfort reported by the subject during the illumination will be recorded by the provided subject's discomfort questionnaire (see [Section 7.3.2](#)).
- Documentation of AEs, including local skin reactions, local discomfort, and pain during and/or after PDT at the treatment field(s).
- Documentation of new AK, NMSC and melanoma, including location of lesion(s).
- Documentation of concomitant medications/treatments including those, which might be taken for pain management during and/or after PDT.
- Subject should be reminded about allowed and forbidden medications (see [Visit 1](#)).

Visit 6, PDT-4 (1-2 weeks –post PDT-3 (Visit 5))

- Assessment of how the subject is feeling since last PDT. Using non-leading questions such as "How did you feel since your photodynamic treatment session", the investigator or delegated person will evaluate any discomfort the subject may be experiencing. Any reported AE or concomitant treatment will be documented.
- Measurement of vital signs (HR and BP).
- Pregnancy test (urine) for females of reproductive potential.
- Thorough preparation of all remaining target lesion(s) included in the study and application of IMP (see [Section 5.1.2](#)).
- Documentation of time of IMP application.
- All lesion(s) that are not yet clinically cleared will be illuminated with an LED lamp (BF-RhodoLED[®]) until a total light dose of 37 J/cm² (per treatment field) is achieved. In cases of severe pain, illumination may be shortly interrupted, e.g. to inject a fast acting local-anesthetic, such as xylocaine (see [Section 5.1.3](#)).
- Documentation of illumination procedures, including time of illumination (10 min) and distance of the LED lamp to the treated lesion(s) (5-8 cm). Additional documentation of possible pain induced interruptions (duration, frequency) and pain relieving measures during illumination. Deviations from the standard illumination procedure have to be justified.

- Pain reported by the subject during the illumination will be recorded using the NRPS by the provided subject's pain questionnaire (see [Section 7.3.2](#)).
- Discomfort reported by the subject during the illumination will be recorded by the provided subject's discomfort questionnaire (see [Section 7.3.2](#)).
- Documentation of AEs, including local skin reactions, local discomfort, and pain during and/or after PDT at the treatment field(s).
- Documentation of new AK, NMSC and melanoma, including location of lesion(s).
- Documentation of concomitant medications/treatments including those, which might be taken for pain management during and/or after PDT.
- Subject should be reminded about allowed and forbidden medications (see [Visit 1](#)).

Phone call 2 (1-week ± 2 days post-PDT-4 (Visit 6))

The aim of this safety telephone contact is to achieve an overall impression on the tolerability of the PDT with the study drug and to evaluate how the subject is feeling since the PDT session. Using non-leading questions such as "How did you feel since your photodynamic treatment session", the investigator or delegated person will evaluate any discomfort the subject may be experiencing. Any reported AE or concomitant treatment will be documented.

The following information will be collected during each phone contact:

- Concomitant medications/treatments.
- (S)AEs and local skin reactions, local discomfort, and pain at the treatment field(s).

Visit 7 (5 weeks ± 1 week post-PDT-3 (Visit 5))

- Assessment of treated BCC target lesion(s) (count, size and location).
- Measurement of vital signs (HR and BP).
- Documentation of AEs, including local skin reactions, local discomfort, and pain at the treatment field(s).
- Documentation of new AK, NMSC and melanoma, including location of lesion(s).
- Documentation of concomitant medications/treatments.

Visit 8 (12 weeks ± 1 week post-PDT-3 (Visit 5))

End of clinical observation period of the study for all subjects that entered a 2nd PDT cycle.

- Assessment of BCC target lesion(s) (count, size, and location).
- Assessment of esthetic appearance of the treated lesions (treatment field(s)) prior to excision of the Main Target Lesion.

- Assessment of subject's satisfaction regarding PDT treatment and esthetic outcome prior to excision of the Main Target Lesion.
- Measurement of vital signs (HR and BP).
- Documentation of AEs, including local skin reactions, local discomfort, and pain at the treatment field(s).
- Documentation of new AK, NMSC and melanoma, including location of lesion(s).
- Documentation of concomitant medications/treatments.
- General physical examination.
- Withdrawal of blood and collection of urine samples for safety laboratory tests and urinalysis.
- Pregnancy test (urine) for females of reproductive potential.
- Excision of the Main Target Lesion (regardless of whether they are clinically cleared or not and only if not already excised at Visit 5) including ink-marks and histological assessment.
- Subjects will be asked to return for the 1st FU visit in approx. 9 months (12 ± 1 months post completion of 1st PDT cycle).
- Treatment of not or partially cleared Additional Target Lesions with conventional therapy at the discretion of the investigator.
- Investigator will send a subject status confirmation by FAX or email.

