7.2.2 End of treatment

The end of treatment is defined as Visit 5 for subjects who were clinically classified as complete responders following the 1st PDT-cycle. For subjects entering a 2nd PDT-cycle (clinically classified as partial- or non-responders at Visit 5), the end of treatment is defined as Visit 8. Depending on the success of the treatment, Main Target Lesions, including the ink marks, will be surgically excised at the respective time point (Visit 5 or Visit 8, respectively). Remaining Additional Target Lesions at Visit 8 will be treated by conventional therapy at the end of this visit. Other reasons for an advanced end of treatment could occur at any time throughout the study due to an AE, withdrawal of consent, or at the discretion of the investigator. After the end of the clinical observation (treatment) part, subjects will enter the FU part of the study. Unscheduled visit(s) may be necessary for aftercare of the excised lesion.

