7.2.3 Follow-up visits

All subjects who completed the clinical observation period in this clinical trial should be followed up for 5 years post-treatment in order to assess the long-term treatment effect with respect to recurrences of the sBCC target lesions and subject's safety. Follow-up (FU) visits will be scheduled 12 ± 1 months, 24 ± 2 months, 36 ± 2 months and 60 ± 2 months after completion of the 1st PDT cycle (Visit 5). Subjects who are drop outs should be encouraged to a final visit for safety documentation.

The following procedures will be performed at FU visits:

- Visual inspection of the treatment fields for any recurrent sBCC target lesion, and determination of size and location in case of recurrence.
- Assessment of esthetic appearance of the treated lesion(s) (treatment field(s)).
- Assessment of subject's satisfaction regarding PDT treatment and esthetic outcome.
- Documentation of relevant (S)AEs (any local AE or conditions within the treatment field(s) that may be relevant for proper assessment of the recurrence of the treated lesions or SAE that impairs the conduct of the study) and related SAEs (SARs) as well as the applicable concomitant medication to treat the relevant AEs/S AEs. Furthermore, any AEs that are considered relevant by the investigator will be documented.
- Documentation of new NMSC and melanoma, including location of lesion(s).
- Documentation of new AK lesions within the treatment field(s) and the treated subarea(s).
- Treatment of recurrent lesions with conventional therapy at the discretion of the investigator.
- The subject will be asked to return for the next follow-up visit, if applicable.
- Investigator will send a subject status confirmation by FAX or email (only for the last regular follow-up visit (FU4).

The results from the FU period of the study will be analyzed and reported separately, and are not part of the clinical observation period of the study.

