11.1.3 Efficacy variables of the FU period of the study

For the FU period of the study, the following analysis variables will be collected and analyzed descriptively and in an exploratory manner:

- Recurrence of the subject's Main Target Lesion after surgical excision (defined as in composite endpoint).
- Subject recurrence rate defined as the percentage of subjects with all Additional Target Lesions completely cleared clinically 12 weeks after the start of the last PDT cycle with at least one recurrent lesion during FU.
- Subject recurrence rate defined as the percentage of subjects with all Additional Target Lesions completely cleared clinically 12 weeks after the start of PDT-1 with at least one recurrent lesion during FU.
- Lesion recurrence rate per treatment arm defined as the percentage of completely cleared individual Additional Target Lesions 12 weeks after the start of the last PDT cycle showing recurrence during FU.
- Lesion recurrence rate per treatment arm defined as the percentage of completely cleared individual Additional Target Lesions 12 weeks after the start of PDT-1 showing recurrence during FU.
- Esthetic appearance for all Main Target Lesions following surgical excision, and for all Additional Target Lesions that were clinically cleared 12 weeks after the last PDT cycle and did not receive additional treatments.
- Subject satisfaction regarding treatment and esthetic outcome for all Target Lesions that did not receive additional treatment after the last PDT cycle.

The results from the FU period of the study will be analyzed and reported separately and are not part of the clinical observation period of the study.

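### The two last-cycle recurrence rates pool lesions with unequal time since clearance, because every follow-up visit is timed from Visit 5

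*Protocol*

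**What the plan says.** Protocol Section 7.2.3 puts every subject on one clock: FU1 at 12 ± 1 months, then "24 ± 2 months, 36 ± 2 months and 60 ± 2 months after completion of the 1st PDT cycle (Visit 5)". Section 7.2.1 shows what this means for the two groups. Complete responders to cycle 1 are told at Visit 5: "Subjects will be asked to return for the 1st FU visit in approx. 12 months". Retreated subjects are told at Visit 8: "Subjects will be asked to return for the 1st FU visit in approx. 9 months". That visit is headed "Visit 8 (12 weeks ± 1 week post-PDT-3 (Visit 5))", so it falls 12 weeks after Visit 5.

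Section 11.1.3 lists four recurrence rates. Two, at subject and lesion level, start from clearance 12 weeks after PDT-1. The other two start from clearance after the last cycle. The lesion-level version is the proportion of cleared "individual Additional Target Lesions 12 weeks after the start of the last PDT cycle showing recurrence during FU". Section 7.3.1 confirms that the qualifying visit may be Visit 5 or Visit 8. Section 11 plans analyses after database locks at 12, 24, 36 and 60 months.

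The length of follow-up is described in several ways:
- Section 7.2.3: subjects "should be followed up for 5 years post-treatment in order to assess the long-term treatment effect".
- Section 7.2.2, for retreated subjects: "the end of treatment is defined as Visit 8".
- Synopsis (study duration), Section 1.2 and Section 8.2: the period is counted from Visit 5.
- Table 1, footnote k: FU4 is placed 60 months after the start of the last PDT cycle.

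The SAP covers the clinical observation phase only and defers follow-up methods to a separate SAP, which is not among the documents.

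**The concern.** A crude percentage at a given visit describes recurrence by a given time only if the lesions in it have been at risk for the same time. In the two last-cycle rates they have not. Lesions cleared at Visit 5 and lesions cleared at Visit 8 enter the same numerator and denominator, and the second group has 12 weeks less observation behind it at every visit. Section 11.1.3 has nothing that adjusts for this.

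Assessing long-term recurrence is a stated purpose of the follow-up. As defined, the last-cycle rates depend partly on how many lesions needed a second cycle. If that share differs between arms, the arm comparison of these two rates also carries some of the difference in timing.

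**Working it through.** **Inputs.** FU visits at 12, 24, 36 and 60 months after Visit 5, with windows of ± 1 month at FU1 and ± 2 months afterwards (7.2.3). Visit 8 at 12 ± 1 weeks after Visit 5 (7.2.1). One-year sBCC lesion recurrence from the EU study: 8.8%, with loss to follow-up counted as recurrence (11.6), or 5.8% (1.1).

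**The plan's own figure.** One month = 365.25/12/7 = 4.348 weeks, so 12 weeks = 12/4.348 = 2.76 months. FU1 after Visit 8 = 12 − 2.76 = 9.24 months, which agrees with the protocol's approximate 9 months. The planned dates agree too: from November 2019 (last subject out of the clinical phase) to August 2024 (last subject out of follow-up) is 57 months, and 60 − 2.76 = 57.24.

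**Time since clearance (months).** The range uses the earliest FU date with Visit 8 at 13 weeks, and the latest FU date with Visit 8 at 11 weeks.

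| Visit | Cleared at Visit 5 | Cleared at Visit 8 | Ratio | Range after Visit 8 |
|---|---|---|---|---|
| FU1 | 12 | 9.24 | 77.0% | 8.01–10.47 |
| FU2 | 24 | 21.24 | 88.5% | 19.01–23.47 |
| FU3 | 36 | 33.24 | 92.3% | 31.01–35.47 |
| FU4 | 60 | 57.24 | 95.4% | 55.01–59.47 |

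The gap is a constant 12 weeks. It applies to the lesion, not to the retreated subject as such: a lesion already clear at Visit 5 in a subject retreated for another lesion is on the correct clock.

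**Size, assuming a constant hazard that is the same for both groups.**
- From 8.8%: hazard = −ln(1 − 0.088)/12 = 0.00768 per month. At 9.24 months, 1 − exp(−0.00768 × 9.24) = 6.85%. The gap at FU1 is 8.80 − 6.85 = 1.95 points; at FU4 the same hazard gives 1.35 points.
- From 5.8%: hazard 0.00498 per month gives 4.50% and a gap of 1.30 points at FU1.
- Lowering of the pooled rate at FU1 = share of cleared lesions that cleared only in cycle 2 × gap. For assumed shares of 10% and 50% with the 8.8% figure: 0.10 × 1.95 = 0.2 and 0.50 × 1.95 = 1.0 points. With the 5.8% figure: 0.13 and 0.65.
- Between arms, a 10-point difference in that share would move the two pooled rates apart by 0.10 × 1.95 = about 0.2 points.

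The hazard assumption fits one historical series better than the other. From 8.8% it predicts 16.8% at two years, against 16% reported. From 5.8% it predicts 11.3%, against 7.7% reported, so for that series it overstates later recurrence.

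**Origin of the five years.** For a retreated subject, FU4 is 57.24 months after Visit 8. Counted from PDT-4, given 1–2 weeks (0.23–0.46 months) after Visit 5, it is 59.54–59.77 months. For a cycle-1 responder, FU4 is 60 months after Visit 5. Footnote k agrees with this for retreated subjects, whose last cycle starts at Visit 5. For cycle-1 responders it points to PDT-1 + 60 months, which is 60 − 2.76 = 57.24 months after Visit 5.

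**The case against.** The clock is declared openly and repeatedly, so the 12-, 24-, 36- and 60-month labels mean time after Visit 5. This stands: the visits are not mislabelled. It does not cure the pooling, because the label says nothing about time since clearance, which is what a recurrence rate needs.

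Visit windows alone allow a spread of two months at FU1 and four months later, more than the 2.76-month gap from FU2 on. That is true of individual visits. But the windows apply to both groups, whereas the 12-week offset runs one way.

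The methods belong to a follow-up SAP that cannot be seen here and may already use time-to-event estimates. This stands as a limit on the point. It cannot be presumed, however, since the protocol defines these variables as percentages.

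The endpoints are descriptive, the lesion rates use Additional Target Lesions only, and the vehicle arm has 37 subjects. Differences of a point or less will not be resolvable there. This also stands, and it sets the severity.

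Three stronger readings are tempting and not supported:
- *All the recurrence rates are distorted.* The two PDT-1 rates share one clock.
- *Five years of follow-up is not delivered.* A shortfall of 2.76 months arises only for retreated subjects, and only if Section 7.2.3 is read through the end-of-treatment definition in 7.2.2. The Synopsis counts the five years from Visit 5, and from PDT-4 the shortfall is 1–2 weeks, within the visit window. What the documents show is a conflict of wording.
- *Recurrence will look lowest in retreated subjects and so favour vehicle.* This needs equal hazards after one and two cycles, and a larger cycle-2 share among cleared vehicle lesions. The documents give neither.

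**Conclusion.** The point holds for the two last-cycle recurrence rates. As written they combine lesions observed for about 9.2 and 12 months at FU1, narrowing in relative terms to 57.2 and 60 at FU4. Under a constant common hazard the effect at FU1 is about 1.3 to 2.0 points for a cycle-2 lesion. Using the 8.8% figure, it is about 0.2 to 1.0 points in the pooled rate if 10 to 50% of cleared lesions cleared only in cycle 2. The 8.8% includes losses to follow-up, so it is not a pure recurrence rate. Any distortion between arms depends on shares that are not given, and its direction cannot be stated.

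Severity is minor. The follow-up variables are exploratory, and the primary and key secondary tests are untouched. It is worth changing because a better definition needs no new visit and no new data.

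**What to change.** In Protocol Section 11.1.3, the parallel lists in the Synopsis and Sections 2.2 and 7.3.1, and the follow-up SAP:

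1. Define the two last-cycle recurrence variables by time from the visit at which the lesion, or the subject, was recorded clear (Visit 5 or Visit 8).
2. Estimate them per arm at fixed times since clearance. Interval-censored methods suit the data best, since recurrence is seen only at widely spaced visits. Kaplan–Meier is simpler, but it dates a recurrence at the visit that found it, so it should be read with the split in item 3.
3. Also report by cycle of clearance.
4. Keep the PDT-1 rates and the visit calendar unchanged.

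Separately, reconcile the statements on the origin and length of follow-up in the Synopsis, Table 1 footnote k, and Sections 1.2, 7.2.2, 7.2.3 and 8.2. This review does not say which origin should prevail.

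The cost is protocol wording, a paragraph in the follow-up SAP and slightly more analysis. The visit dates are collected anyway. The longest horizon common to all lesions becomes about 57 months since clearance.
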